## 6.2. Clinical Laboratory Tests

All clinical laboratory reports will be displayed for the participants included in the safety analysis set. The clinical laboratory parameters to be evaluated by the central laboratory include but are not limited to:

- **Hematology:** Basophils, Eosinophils, Hemoglobin, Lymphocytes, Monocytes, Neutrophils, Platelets and WBC.
- **Chemistry:** Albumin, Alkaline Phosphatase, Bicarbonate (CO2), Calcium, Chloride, Creatinine, GGT, Glucose, Potassium, SGOT, SGPT, Sodium, Total Bilirubin, Total Protein, Urea Nitrogen.

Box plots of laboratory measurements and change from baseline will be provided for the selected laboratory measurement.

Applicable laboratory results will be graded according to National Cancer Institute's Common Terminology Criteria for Adverse Events (NCI-CTCAE version 5.0). The worst NCI-CTCAE will be summarized by treatment group.

A listing of participants with 1 or more NCI-CTCAE toxicity grade  $\geq$ 2 in hematology and clinical chemistry laboratory measurements will be provided.

### 6.3. Vital Signs and Physical Examination Findings

Vital signs including pulse, blood pressure (systolic and diastolic), body temperature, peripheral blood oxygen saturation (SpO2) and respiratory rate will be measured at visits (pre-injection and post-injection) as per the schedule of activities in the protocol. Descriptive statistics of the observed value and change from baseline of the vital signs will be summarized by treatment group over time.

Physical exam findings will not be analyzed. When physical exam findings are captured as AEs, those will be included in the analyses of AEs.

## 7. PHARMACOKINETICS/PHARMACODYNAMICS

Blood was drawn into three 6 ml collection tubes at each specified time point. These samples will be used for PK, immunogenicity, PD, biomarker, and general research analyses.

### 7.1. Pharmacokinetics

All PK analyses will be based on the PK analysis set (Section 2.4.3). Participants will be analyzed according to the randomized treatment groups they were assigned to, regardless of the treatments they actually received. Unless otherwise specified, tabular summaries of PK for key study periods are in general presented as following:

#### Summaries through Week 16:

PK data through Week 16 will be summarized by treatment groups

- Bermekimab 400 mg q2w
- Bermekimab 400 mg qw

#### Summaries through Week 36:

PK data through Week 36 will be summarized by treatment groups including

- Placebo → Bermekimab 400 mg qw
- Bermekimab 400 mg q2w
- Bermekimab 400 mg qw

#### 7.1.1. Bermekimab Concentrations

Bermekimab concentrations will be summarized using descriptive statistics, including n, arithmetic mean, SD, coefficient of variation (%CV), median, interquartile range, range (minimum and maximum), by treatment group at each PK sampling time where appropriate. PK data may be displayed graphically. The following analyses will be performed as appropriate:

- Summary of bermekimab concentrations at each visit by treatment group

- Proportion of participants without detectable bermekimab concentration (below the lower limit of quantification) at each visit by treatment group
- Summary of bermekimab concentrations at each visit by treatment group and baseline body weight (quartiles). Other covariates may also be applied.
- Summary of bermekimab concentrations at each visit by treatment group and baseline EASI severity.
- Plot of mean (SD) bermekimab concentrations over time by treatment group
- Plot of median (IQ) bermekimab concentrations over time by treatment group

#### 7.1.1.1. Data Handling Rules

Unless otherwise specified, the following data handling rules will apply to PK analyses:

- Participants will be analyzed according to the treatment groups that they actually received.
- All concentration summaries for a particular timepoint will include data obtained from treated participants at the timepoint of interest without imputing any missing data.
- A concentration not quantifiable (below the lower limit of quantification) will be treated as 0 in the summary statistics and shown as the lower limit of quantification (< LLOQ) in the data listings.
- The data from a subject who meets 1 of the following dosing deviation criteria (if applicable) will be excluded from the by-visit data analyses from that point onwards:
  - Discontinue bermekimab administrations.
  - Skipped a bermekimab administration.
  - Received an incomplete/ incorrect dose (if applicable).
  - Received an incorrect study agent (if applicable).
  - Received an additional bermekimab dose.

In addition, if a subject has an administration outside of dosing windows (Table 2), the concentration data collected at and after that visit will be excluded from the by-visit data analyses. Additional exclusions for incongruous PK data to be implemented based on Janssen SOP-07948. All participants and samples excluded from the analysis will be clearly documented in the Clinical Study Report.

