## 5.2.2 Blinded Active Dosing Period

Study Procedure	Blinded Active Dosing Period																
	V18	V19	V20	V21	V22	V23	V24	V25	V26	V27	V28	V29	V30	V31	V32	V33	
Visit (V)	W17	W18	W19	W20	W21	W22	W23	W24	W25	W26	W27	W28	W29	W30	W31	W32	
Week (W)	D119	D126	D133	D140	D147	D154	D161	D168	D175	D182	D189	D196	D203	D210	D217	D224	
Day (D)	Visit Window (d)																
Treatment: 	±3d																
Administer Study Drug	X	X	X	X	X	X	X	X	X	X	X	X	X	X	X	X	
Con Meds/ Treatments	X	X	X	X	X	X	X	X	X	X	X	X	X	X	X	X	X
Efficacy:																	
Patient Diary (daily)	X	X	X	X	X	X	X	X	X	X	X	X	X	X	X	X	X
IGA, EASI, GISS, SCORAD, BSA				X				X				X				X	
POEM, DLQI, HADS				X				X				X					X
Safety:																	
Physical Examination																	X
Electrocardiogram																	
Vital Signs	X	X	X	X	X	X	X	X	X	X	X	X	X	X	X	X	X
Adverse Events	X	X	X	X	X	X	X	X	X	X	X	X	X	X	X	X	X
Laboratory Testing:																	
Infectious Disease Panel																	
Hematology, Chemistry, Inflammation Markers								X									X
Urinalysis								X									X
Pregnancy Test (WOCBP only)	X	X	X	X	X	X	X	X	X	X	X	X	X	X	X	X	X
PK/PD/ADA:																	
PK/ADA, IL-6, PD, biomarker & research samples (serum/plasma)								X									X

 Patients will be monitored at the study site at visits 1, 2, 3, 17, 18 & 19 (weeks 0, 1, 2, 18, 19 & 20) for a minimum of 30 minutes after study drug administration. Vital signs and AE assessments will be done at 30 minutes (+/- 10 minutes) post-injection.

 Patients will be randomized to treatment arm 1, 2, or 3 and will follow the corresponding treatment plan.

 Assessments/procedures should be conducted in the following order: patient assessments, investigator assessments, safety and laboratory assignments, administration of the study drug.

 Concomitant medications within 30 days before screening until 7 days after the last administration of the study drug must be recorded for the purpose of drug-drug and drug-disease interaction evaluation and signal detection

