### 1.2. Trial Design

This is a phase II, randomized, double-blind, placebo-controlled study to further establish the efficacy, safety, PK, and explore dose effects for bermekimab monotherapy in adults with moderate to severe Atopic Dermatitis (AD). The participant population will comprise men and women who have had chronic atopic dermatitis present for at least 3 years. The study is approximately 40 weeks (30 day screening period, 32-week treatment period and a 4-week follow-up period) for all subjects.

A diagram of the study design ([Figure 1](#)) is provided below, approximately 90 patients who meet the eligibility criteria at screening will be randomized in a 1:1:1 ratio to one of two active treatment arms or placebo:

- Arm 1: 400 mg loading dose of bermekimab (2mL SC injection containing 400 mg of bermekimab and one 2mL SC injection of placebo) at Week 0 followed by weekly (qw) subcutaneous (SC) injections of 400 mg bermekimab through Week 31
- Arm 2: 800 mg loading dose of bermekimab (2 x 400 mg SC injections) at Week 0 followed by subcutaneous (SC) injections of 400 mg bermekimab every other week (q2w) alternating with matching placebo q2w through Week 31.

- Arm 3: 4mL loading dose of placebo (2 x 2mL SC injections) at Week 0 followed by weekly placebo injections from Week 1 through Week 15. Patients in Arm 3 will begin to receive weekly (qw) blinded subcutaneous (SC) injections of 400 mg bermekimab beginning at Week 16 through Week 31.

Patients will be monitored at a follow up visit (week 36) for safety and clinical assessments after completing the 32 week treatment period.

Efficacy assessments include Eczema Area and Severity Index Score (EASI) score, Itch Numerical Rating Scale (NRS), Pain NRS, Severity Scoring of Atopic Dermatitis (SCORAD), Patient Oriented Eczema Measure (POEM), Global Individual Signs Score (GISS), Dermatology Life Quality Index (DLQI), Hospital Anxiety Depression Scale (HADS), Body Surface Area (BSA) and Investigator's Global Assessment (IGA) will be performed according to the Study Calendars (Section 5.2 of the protocol).

Blood samples will be collected for laboratory testing including chemistry, hematology, inflammation markers, bermekimab concentration (PK), PD marker(s), and anti-drug antibody (ADA).

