### 1.5.2. Maintenance of Blind

The study blind will be maintained for the duration of the study, until after the Final (Week 36) DBL.

In order to maintain blinding, all patients will receive two injections at Week 0, followed by weekly injections from Week 1 to 31. Additionally, to ensure that no unintentional unblinding occurs during study drug administration, a qualified individual will be designated at each study site to perform all preparation and injection of the investigational product. The designated injector should have no other contact with the participant during the study, should not discuss the participant's treatment with the participant, participant's caregiver, or other site personnel at any time, and will not be permitted to review the participant's medical records, questionnaires, or the electronic CRF prior to each injection. The designated injector should be documented in the source documents at each visit.

The investigator will not be provided with randomization codes. The codes will be maintained within the Electronic Data Capture (EDC) system, which has the functionality to allow the investigator to break the blind for an individual participant.

Data that may potentially unblind the intervention assignment (ie, study intervention serum concentrations, anti-bermekimab antibodies, and intervention allocation) will be handled with special care to ensure that the integrity of the blind is maintained and the potential for bias is minimized. This can include making special provisions, such as segregating the data in question

from view by the investigators, clinical team, or others as appropriate until the time of DBL and unblinding.

Under normal circumstances, the blind should not be broken until all participants have completed the study and the database is finalized. However, a number of prospectively identified Sponsor individuals will be unblinded at the Week 16 DBL. Identification of sponsor personnel who will have access to the unblinded data at subject-level and who will have access to the unblinded data at group-level will be documented prior to unblinding at the Week 16 DBL. All site personnel and participants will remain blinded to the treatment assignments until the last participant completes Week 36 evaluations and the database has been locked.

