**Table 2: Dosing Window**

Visit	Window
Week 0 through Week 32	± 3 days from scheduled visit day
Final Safety and Efficacy Follow-up visits Week 36	± 7 days from scheduled visit day

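### The PK dosing-window exclusion in SAP 7.1.1.1 is not limited to bermekimab injections, so read literally a mistimed placebo injection removes valid later bermekimab concentrations

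*SAP*

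**What the plan says.** SAP 7.1.1.1 (Data Handling Rules, under Bermekimab Concentrations) first lists five dosing deviations after which a participant's data leave the by-visit analyses. Three of the five name bermekimab: discontinuing it, receiving an additional dose of it, and "Skipped a bermekimab administration". The other two, an incomplete or incorrect dose and an incorrect study agent, do not name it.

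A separate sentence then adds the window rule: "if a subject has an administration outside of dosing windows (Table 2), the concentration data collected at and after that visit will be excluded". SAP Table 2 sets the window at ±3 days for "Week 0 through Week 32" and draws no line between active and placebo visits.

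The regimens are in SAP 1.2 and 1.5.2:

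- All arms receive two injections at Week 0, "followed by weekly injections from Week 1 to 31".
- Arm 2 receives bermekimab "every other week (q2w) alternating with matching placebo q2w through Week 31".
- Arm 3 receives "weekly placebo injections from Week 1 through Week 15" and starts bermekimab at Week 16.

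SAP 2.4.3 (the PK analysis set) and SAP 7.1 neither limit the window rule to active doses nor restart it at the Week 16 crossover. The Week 36 PK summaries in SAP 7.1 cover all three groups. The Week 16 summaries cover the two groups randomized to bermekimab.

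**The concern.** The timing of a placebo injection cannot alter a bermekimab concentration. A rule that drops all later concentrations because a placebo injection was mistimed therefore discards valid data.

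It also treats two placebo deviations inconsistently. A mistimed placebo injection ends the participant's contribution to the by-visit analyses, while a missed one has no effect because the skipping criterion is confined to bermekimab.

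Arm 3 is the most exposed. Protocol 5.2.2 and 5.2.3 schedule its PK samples after the first bermekimab dose at Weeks 24, 32 and 36 only, since the Week 16 draw is taken before the injection. One trigger during the placebo phase removes all three.

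PK is part of a secondary objective (SAP 1.1). SAP 7.1.1 also splits the summaries by body-weight quartile and baseline EASI severity. From about 30 participants per arm, those cells start at roughly 7 (30/4 = 7.5) to 15 (30/2, if the strata are equal), so a few needless exclusions would show.

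**Working it through.** The plan gives no figure for out-of-window injections or expected PK exclusions, so there is nothing of its own to reproduce on this point. Two things can be checked: which injections can trigger the rule, and how much that could matter under stated assumptions.

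**Step 1. Placebo injections among the post-baseline injections (Weeks 1 to 31).**

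| Arm | Injections | Placebo | Bermekimab |
|---|---|---|---|
| 1 (qw) | 31 | 0 | 31 |
| 2 (q2w) | 31 | 15 or 16 | 16 or 15 |
| 3 (placebo to qw) | 31 | 15 (Weeks 1–15) | 16 (Weeks 16–31) |

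The Arm 2 split depends on whether active doses fall in odd or even weeks, which the SAP does not state. These counts rest on no assumed rate.

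**Step 2. When the trigger can fire.** Visits are 7 days apart with ±3-day windows, so adjacent windows abut. Week 5 is Day 35 (window Days 32–38) and Week 6 is Day 42 (window Days 39–45). A Week 5 placebo injection given 4 days late falls on Day 39, the first day of the Week 6 window. The rule fires if that injection keeps its Week 5 label. It does not fire if the site records a missed Week 5 and an in-window Week 6.

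**Step 3. Illustrative size in Arm 3.** Assumptions: a per-visit out-of-window probability p of 1%, 2% or 5%, 30 participants (90/3), and no dropout, other exclusion or missing sample. Exclusion runs forward from the trigger, so losing the Week 24 sample means losing all three.

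- As written, the triggers are Weeks 1–24, so k = 24.
- Limited to bermekimab, the triggers are Weeks 16–24, so k = 9.

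If visits are independent, loss = 1 − (1 − p)^k. At p = 0.02 this is 1 − 0.98^24 = 0.384 against 1 − 0.98^9 = 0.166.

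If mistimed visits cluster within participants with correlation ρ, a beta-binomial model gives loss = 1 − B(a, b + k)/B(a, b), where B is the beta function, a = p(1/ρ − 1) and b = (1 − p)(1/ρ − 1). At p = 0.02 and ρ = 0.1, a = 0.18 and b = 8.82, and the loss is 0.216 against 0.123.

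| Model | p | As written | Bermekimab only | Extra loss (points) | Of 30 |
|---|---|---|---|---|---|
| ρ = 0.2 | 1% | 7.9% | 5.0% | 3.0 | 0.9 |
| | 2% | 15.2% | 9.7% | 5.5 | 1.7 |
| | 5% | 34.1% | 22.8% | 11.3 | 3.4 |
| ρ = 0.1 | 1% | 11.4% | 6.3% | 5.1 | 1.5 |
| | 2% | 21.6% | 12.3% | 9.3 | 2.8 |
| | 5% | 45.8% | 28.2% | 17.6 | 5.3 |
| Independent | 1% | 21.4% | 8.6% | 12.8 | 3.8 |
| | 2% | 38.4% | 16.6% | 21.8 | 6.5 |
| | 5% | 70.8% | 37.0% | 33.8 | 10.1 |

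**Step 4. Arm 2, independent visits only.** At Week 16 the loss as written (k = 16) is 14.9%, 27.6% or 56.0%. Limited to the 8 active doses it is 7.7%, 14.9% or 33.7%. If Week 16 is a placebo visit and its late sample is dropped too (k = 9), it is 8.6%, 16.6% or 37.0%. At Week 36 the loss as written (k = 31) is 26.8%, 46.5% or 79.6%, against 14.0–14.9%, 26.1–27.6% or 53.7–56.0% with 15 or 16 active doses. Clustering would shrink these differences as well. Arm 1 is unchanged under either wording.

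**The case against.** The strongest reply is that the intended meaning is clear from context. The rule sits under a heading about bermekimab concentrations, follows criteria of which three of five name bermekimab, and applies to an analysis set defined from the first bermekimab dose. That makes a bermekimab-only intent plausible. It does not settle the wording: the qualifier stands in neighbouring criteria and is absent here, and a programmer working from the text could apply the rule to every injection.

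Second, the trigger may be rare. Because the windows abut, some late placebo injections would be recorded as a missed visit plus an in-window one. SAP 2.2 requires contact with the sponsor over significant scheduling deviations. The protocol's COVID-19 appendix expects delayed visits, but on a weekly schedule a long delay would often become a missed injection, and the appendix also allows dosing at home. All of this stands, and it is why 1% to 5% is only an illustration.

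Third, dropout and other exclusions remove data under either wording. If only 23 of 30 remained at Week 24, the independent 2% case would keep 14.2 rather than 19.2 participants (23 × 0.616 and 23 × 0.834), a difference of 5.0 rather than 6.5. This stands too.

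Fourth, SAP 7.1.1.1 requires exclusions to be documented in the study report, so a misapplied rule would be visible and could be rerun. That limits the harm, but the tabulated summaries would still lack the data.

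Finally, a sample drawn at a late placebo visit is itself off its nominal time. That justifies dropping that sample, not the later ones.

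**Conclusion.** The point holds as a minor drafting correction. As worded, the rule lets a mistimed placebo injection in Arm 2 or Arm 3 remove valid later concentrations, and nothing in the PK sections prevents that reading. About half of the post-baseline injections in those arms are placebo and should not count.

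The size is uncertain. Mistimed visits probably cluster within participants, so the 3 to 18 point range is the more credible illustration for Arm 3, with 13 to 34 points under independence as an upper case. Both rest on assumed rates, and the clustered range also on assumed correlations. Neither allows for dropout or other exclusions.

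A reader might infer from the larger percentages that most Arm 3 PK data will be lost, or that any placebo injection four days late triggers the rule. The documents support neither: they give no out-of-window rate, and whether the rule fires depends on how the visit is labelled. Nor do they show that the authors meant to include placebo.

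Only the descriptive by-visit PK summaries are affected. The primary endpoint, its type I error and its power are untouched, as is any population PK analysis under SAP 7.1.3.

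**What to change.** In SAP 7.1.1.1:

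- Make the window sentence refer to a bermekimab administration outside the Table 2 windows. For Arm 3 the rule then starts at Week 16.
- State that the incomplete or incorrect dose criterion means bermekimab doses.
- Leave the incorrect study agent criterion as it is, because a wrong agent given in a placebo slot may be bermekimab.
- Where a mistimed placebo visit is also a PK sampling visit, flag or drop only that visit's sample.
- Report the number excluded and the reason by arm.

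The cost is a few words and no new data. There are two consequences. Exclusion rates will differ by arm, because Arm 1 has 31 post-baseline active doses against 15 or 16 in the other arms, which is why the by-arm display is needed. The analysts will also need the identity of each injection at each database lock, when those running the PK summaries are unblinded.

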**Table 2: Dosing Window**

Visit	Window
Week 0 through Week 32	± 3 days from scheduled visit day
Final Safety and Efficacy Follow-up visits Week 36	± 7 days from scheduled visit day

### **7.1.2. PK vs Efficacy**

The relationship between bermekimab concentrations and efficacy endpoints may be explored, e.g.:

- The relationship between bermekimab concentrations (quartiles) and proportion of participants achieving EASI-75

### **7.1.3. Population PK Analysis**

When appropriate, population PK analysis may be performed using bermekimab concentration-time data with the nonlinear mixed-effects modeling (NONMEM) approach. Details will be provided in a separate technical report.

## **7.2. Immunogenicity**

Immunogenicity analyses will be based on the Immunogenicity Analysis Set (Section 2.4.5). Participants will be analyzed according to the randomized treatment groups they were assigned to, regardless of the treatments they actually received. No imputation for missing concentration data will be performed.

Immunogenicity data through Week 36 will be summarized by treatment groups including

- Placebo → Bermekimab 400 mg qw
- Bermekimab 400 mg q2w
- Bermekimab 400 mg qw
- Combined Bermekimab

### **7.2.1. Antibodies to Bermekimab**

Blood samples will be collected to examine the formation of anti-drug antibody (ADA) to bermekimab at the specified visits as shown in the schedule of activities in the protocol. Samples will also be collected at the final visit from participants who terminate study participation early.

The antibodies to bermekimab status (positive/negative) and titers will be summarized by treatment group for participants who receive at least one dose of bermekimab and have appropriate samples for detection of antibodies to bermekimab. The maximum titers of antibodies to bermekimab will be provided for participants who are positive for antibodies to bermekimab.

A listing of participants who are positive for antibodies to bermekimab will be provided. This listing will provide information regarding dose administered, bermekimab concentration, and antibody status for all visits.

---

### 7.2.2. **Antibody vs PK/Efficacy/Safety**

To explore the relationship between antibodies to bermekimab status and bermekimab concentrations, efficacy and safety, the following analysis may be performed if sufficient numbers of participants are positive for antibodies:

- Summary of bermekimab concentrations by antibodies to bermekimab status
- Plots of mean (SD) trough bermekimab concentrations over time by antibodies to bermekimab status
- Summary of clinical response status (e.g., proportion of participants achieving EASI-75) by antibodies to bermekimab status
- Summary of injection-site reactions by antibodies to bermekimab status (if applicable)
- List of antibodies to bermekimab status in participants who discontinued study early

### 7.3. **Biomarkers**

Biomarker assessments will include the evaluation of relevant markers in serum for all participants. The samples will be used to better understand the biology of AD in some or all of the following ways: to provide mechanistic assessment of the pharmacodynamic response of participants to treatment with bermekimab, to analyze differences between responders and nonresponders, and to determine if the markers might be used to classify participants as potential responders prior to treatment.

Serum samples will be analyzed for circulating factors such as cytokines and other inflammatory markers, and other categories of biomarkers potentially associated with the development and progression of AD or related to the bermekimab mechanism of action. These analyses are considered exploratory and will be summarized in a separate biomarker technical report.

